5.2 Exclusion criteria

Participants will be excluded if they:

- Currently use a dietary salt substitute
- Currently use the FoodSwitch app
- Have a contraindication to changing dietary sodium or potassium intake e.g. severe kidney disease or use a potassium sparing diuretic
- Are taking medication that may lead to hyponatraemia or acute build-up of body water such as furosemide, regular NSAID use, or regular prednisone use
- Have had a stroke or cardiovascular event (hospitalisation for heart attack, coronary artery revascularisation (CABG or stenting), stroke or heart failure) in the previous 6 months
- Have diagnosed heart failure

5.3 Recruitment

Participants will be recruited using four main methods:

- (1) Face-to-face recruitment at Green Cross pharmacies, in shopping malls, at local events and markets, and in the Stroke Foundation blood pressure van.
- (2) Through Green Cross and other GP clinics/primary care providers that the researchers have existing relationships with e.g. The Fono
- (3) Using social media e.g. Facebook, where adverts will be targeted to the characteristics of the intended study population and information given to direct people to Green Cross pharmacies or their local health provider to have their BP taken or a screening clinic at The University of Auckland's Grafton Campus
- (4) Via market research panels where a survey is sent to the panel and those who are interested can complete some questions about their eligibility and supply contact details; they will then be invited to attend a screening clinic at Grafton Campus or directed to a Green Cross pharmacy or their local health provider to obtain BP measurements.

We will make every effort to employ Māori and Pacific Research Assistants (RAs) for recruitment of participants in shopping malls, and these same staff members will follow up participants by telephone throughout the study. Text messages inviting people registered with Green Cross for their prescriptions may also be used, and leaders of Māori communities NIHI has existing relationships with may be approached to increase recruitment of Māori. Recruitment will start in the Auckland region but may extend to other regions, if required to meet recruitment targets. Recruitment will be targeted to regions with higher proportions of Māori and low-income residents. Potential participants will watch a short study video and/or have the study explained to them either at the shopping mall, pharmacy or by their healthcare provider. A referral form will be completed where weight, BP, and smartphone ownership will be recorded. Interested people with a SBP

Not for Public Circulation or Reproduction

≥140mmHg and/or DBP≥85mmHg who own a smartphone (iPhone or Android) will provide a phone number and email address and consent to their details being forwarded to a study RA, who will call and administer a screening questionnaire to confirm eligibility.

5.4 Study intervention

Both groups (intervention and control) will receive a study smartphone app (compatible with iOS and Android). All participants who are randomised will be allowed to keep the Wi-Fi enabled BP monitor provided during the trial for home-based BP measures.

Intervention group

The intervention group will receive (in addition to the study app) the SaltSwitch smartphone app and a supply of low sodium high potassium dietary salt substitute, each component of the intervention targeted at a different source of dietary sodium.

The SaltSwitch app helps users to select lower salt packaged foods by enabling them to scan the

barcode of a packaged food and receive an immediate, interpretive traffic light nutrition label on-screen plus suggestions for lower salt alternatives (Figure 1). Users can also directly compare the salt content and healthiness of two or more food products. The traffic light nutrition criteria underpinning the app are sourced from the UK traffic light nutrition labelling system²⁸, and the tool used to rank foods by how healthy they are is the Australasian Nutrient Profiling Scoring Criterion (NPSC)²⁹. SaltSwitch was originally developed by the George Institute for Global Health in Sydney, and has been adapted for NZ shoppers using the Nutritrack food composition database; it is a filter for the generic FoodSwitch app currently available for free in the NZ app store (iOS and Android). However, the Nutritrack food product database underpinning the app has not been updated since 2016, thus limiting the utility of the publicly available version. Participants in the intervention group will receive a link in a text message to download the SaltSwitch app in the NZ iOS and Android app stores. A code will be provided to unlock the app ensuring participants outside of the study will not contribute to Google Analytics data; this will also decrease the likelihood of participants in the control group accessing the app. Once downloaded the SaltSwitch app will take the user through a brief tutorial on how to use the app to make healthier, lower salt food choices.

Figure 1: SaltSwitch app

Not for Public Circulation or Reproduction

The dietary salt substitute targets discretionary (added) sodium. Participants will receive two 79g bottles of 'Salt for Life' comprising a blend of potassium salt and sea salt, which provides a 75% reduction in sodium compared to regular table salt and comprises 74.5% potassium chloride, 24.5% sodium chloride, and ~1% silicon dioxide (anticaking agent). Two bottles/shakers will enable participants to have one for use in the home, and a second saltshaker for mobile use e.g. to replace salt usually added at a restaurant or café. The salt substitute is shown in Figure 2 in its branded packaging but will be provided in plain packaging for study participants. Nutek are providing the salt substitute for use in the study, but do not otherwise have any involvement in the research. The salt substitute provided in the trial is not currently available for sale in New Zealand pharmacies or any other locations (although similar products such as [name] Sodium Salt are available for sale in some New Zealand supermarkets).

[figure not shown]

Figure 2: Salt for Life salt substitute

Control group

Participants randomised to the control group will receive the study smartphone app which will send a notification after randomisation (i.e. at week 1) with links to publicly available information on heart-healthy eating information on the Heart Foundation of New Zealand website³⁰. The study app will also provide notifications to participants to remind them to measure their BP during the study (week -1, 6, and 12).

5.5 Randomisation

Eligible participants will be randomised at the beginning of week 1 via a centralised randomisation system. All participants will be randomised in a 1:1 ratio to the intervention or control group, stratified by ethnicity (Māori and non-Māori) and age (<55yrs and 55yrs+) using stratified block randomisation with variable block sizes of two or four.

The RA will activate randomisation for each participant, which will ensure receipt of the correct notifications from the study smartphone app (i.e. intervention or control). The RA will text participants to notify them of the group they have been randomised to and provide the intervention group their SaltSwitch access code. The RA will then call participants in the intervention group to help download and unlock the SaltSwitch app and watch the tutorial. Following the randomisation phone call a study RA will courier a supply of study salt to those in the intervention group.

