5.6 Blinding

It is not possible to blind study participants or researchers to who receives the salt reduction intervention. The study investigators will have no access to treatment allocations during the study. The primary and secondary outcomes will be measured objectively using home-based BP monitors, urine samples and scanned barcodes of packaged foods and beverages purchased, the latter which will be linked to a packaged food composition database to determine the sodium contents.

Not for Public Circulation or Reproduction

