Notification of randomisation (contact 3 – text message)

At the end of baseline (end of week -1), a study RA will confirm eligibility (minimum of six BP measures received, one urine sample, and 10 scanned food purchases) and text the participant (contact 3) to notify them of the group they have been allocated to. The RA will activate the participants study smartphone app to receive the appropriate notifications, based on their allocation. The RA will call participants in the intervention group to support them download the SaltSwitch smartphone app, enter a code to 'unlock' it, and watch a short tutorial (within the app) on how to use it. The intervention group will be notified that they will receive a supply of study salt in the mail.

Study end (contact 4 – a. Phone call and b. Email/Letter)

Participants will receive a notification via the study app at the end of week 12 to complete the follow-up questionnaire. If the follow up questionnaire has not been completed within one week following the end of the study, a follow-up phone call(s) (contact 4a.) may be required. On completion of the follow up questionnaire participants will receive a notification thanking them for their participation, a summary of their BP measures over the study, and more information about the dietary salt substitute. A study completion email or letter (contact 4b.) will also be sent to participants which will include instructions (1) to download the BlipCare smartphone app to monitor their BP measures post study-completion (2) to change the settings in their phone to enable them to continue using the SaltSwitch app but to cease collection of their use of the app by Google Analytics if in the intervention group (3) to download the SaltSwitch app (control group) and on how to purchase the dietary salt substitute. The RA will disconnect the participant's blood pressure monitor from the study system to stop data being sent to the study team.

Not for Public Circulation or Reproduction

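### Blocks of two or four, printed in an open-label protocol whose research assistants confirm baseline criteria, trigger randomisation and see allocations, leave concealment of the next allocation not assured

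*Protocol*

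**What the plan says.** Section 5.5 places randomisation at the start of week 1 through a centralised system, 1:1, in four strata (Māori or non-Māori, under 55 or 55 and over), "using stratified block randomisation with variable block sizes of two or four". There is no site stratum. The same section says "The RA will activate randomisation for each participant" and "The RA will text participants to notify them of the group they have been randomised to"; the RA then phones intervention participants, and a study RA couriers the salt substitute to them.

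Section 5.20 says that at the end of baseline "a study RA will confirm eligibility" against three minimum counts (home BP readings, urine sample, scanned purchases) and, in the same step, texts the participant the allocation.

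Section 5.6 states: "It is not possible to blind study participants or researchers to who receives the salt reduction intervention". Sections 5.6 and 8.4 keep allocations from the study investigators only. Nothing keeps RAs from seeing earlier allocations or the block sizes.

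**The concern.** Central generation hides the list. It does not hide what can be worked out from allocations already made. Every block ends balanced, so the arm that is behind in a stratum is always the better guess for the next participant, and with blocks of two or four that guess is often right. The RAs see the earlier allocations and also act at the point of entry.

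If the next arm can be predicted, the order in which waiting participants are randomised, the handling of an incomplete baseline, or the effort spent on getting someone to complete it could follow the predicted arm. That would be selection at entry. Objective outcome measurement does not correct it, and adjustment for baseline and strata deals only with what has been measured, not with traits such as motivation.

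**Working it through.** **Inputs.** From section 5.5: block sizes 2 and 4, ratio 1:1, four strata. From section 6.1: 326 participants, or about 82 per stratum if the strata are equal (an assumption). The mix of block sizes is not stated, so P(block of 2) is taken as 0.50, with 0.25 and 0.75 as a range.

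**The plan's own figure.** The protocol gives no figure for predictability. The sample size only scales the counts below, and it reproduces: 2 × (1.960 + 0.842)² / 0.33² gives 145 per arm, 145 / 0.9 gives 162, and so 324 in total against 326 stated. Nothing in this point changes it.

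**Correct guesses, one observer of the whole stratum history.** The observer guesses the arm that is behind and tosses a coin at balance. For a block of size 2m the expected number correct is m + ½ × (4^m / C(2m, m) − 1).

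- Block of 2: 1 + ½ × (4/2 − 1) = 1.5
- Block of 4: 2 + ½ × (16/6 − 1) = 2.833
- Equal mix: (1.5 + 2.833) / (2 + 4) = 72.2%
- P(block of 2) = 0.25: (0.375 + 2.125) / 3.5 = 71.4%
- P(block of 2) = 0.75: (1.125 + 0.708) / 2.5 = 73.3%

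**Every second allocation.** In a block of 2 the second is always right (1 of 1). In a block of 4 the second is right with probability 2/3 and the fourth always (5/3 of 2). Equal mix: (1 + 5/3) / 3 = 88.9%.

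**Allocations known for certain.** This needs knowledge of the sizes. Two like allocations running from balance can only open a block of 4, so the next two are fixed. That happens in 2 of the 6 possible blocks of 4, which gives 2 × 1/3 = 2/3 certain allocations per block of 4. Equal mix: (½ × 2/3) / 3 = 11.1%. For the other mixes: (0.75 × 2/3) / 3.5 = 14.3% and (0.25 × 2/3) / 2.5 = 6.7%. Simulation with 82 per stratum gives 10.7%, 14.0% and 6.4%. At 10.7% this is 0.107 × 326, about 35 participants.

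**If RAs do not share results.** I simulated two or three RAs who split a stratum at random, each using only the allocations that RA has seen, by one of two simple rules (guess the arm that is behind, or the opposite of the last one seen). Two RAs score about 54% to 60%, three about 53% to 57%. The number of RAs is an assumption.

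**Blocks of 4, 6 and 8, equally likely, full history.**

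- Expected correct for 6: 3 + ½ × (64/20 − 1) = 4.1; for 8: 4 + ½ × (256/70 − 1) = 5.329
- Overall: (2.833 + 4.1 + 5.329) / 18 = 68.1%
- Every second allocation: (1.667 + 2.3 + 2.914) / 9 = 76.5%
- Certain, by simulation: 2.4%, or 0.024 × 326, about 8 participants

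**Hiding the sizes alone.** Guessing the arm that is behind uses no knowledge of block size. The simulated rate for blocks of 2 and 4 is 72% with or without that knowledge. Non-disclosure removes certainty and leaves the best-guess rate where it is.

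**The case against.** The strongest reply is that the RAs have little to act on. Consent and clinical eligibility are settled earlier. The end-of-baseline check is three counts, with BP readings arriving automatically and barcodes through the app. Section 11.3 sets randomisation two weeks after the baseline questionnaire. Section 5.13 has urine samples sent in bulk to another university, so baseline sodium is probably unknown when randomisation is activated, and the primary model in section 6.2.2 adjusts for baseline and strata. The protocol also speaks of several RAs and nowhere says that one person sees every allocation. Block size already varies, and small blocks buy balance in four strata.

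All of this stands, and it makes the opening narrow. It does not close it. Collection windows around baseline run to plus or minus two weeks, so there is some slack in when a participant is complete. The rule for an unreturned baseline urine sample conflicts: section 5.13 treats it as missing data, while section 5.20 requires a sample before randomisation. That leaves a judgement at the moment of entry. Nothing in the protocol separates the RAs' knowledge. Varying the size cuts certainty (about 33% for fixed blocks of 4) but hardly changes guessing (about 71%).

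A reader might go further and infer that concealment fails in practice, or that every outcome is biased. The documents do not support that. Even for the best-placed observer about 89% of allocations are not certain, and nothing shows that anyone predicts or steers.

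**Conclusion.** The point holds as a weakness in the protection against selection bias. Allocation concealment is not assured, although the list is central. With shared stratum histories and an equal block mix, about 72% of allocations can be guessed (71% to 73% over the other mixes) and about 11% are certain (6% to 14%). These are upper-end figures; without sharing between two or three RAs, simple rules give roughly 53% to 60%, against 50% by chance. Significance level, power and sample size are unaffected. The change is worth making because it is cheap, not because bias has been shown.

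**What to change.** For all remaining randomisations:

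1. Drop blocks of two and use larger, randomly varying blocks, for example 4, 6 and 8. With full information, certain allocations fall from about 11% to about 2%, correct guesses of every second allocation from 89% to about 76.5%, and overall correct guesses from 72% to 68%. The gain is mainly in certainty; the overall rate moves little.
2. Take the sizes out of section 5.5 and keep them in a document that the RAs do not see. This removes certainty only, so it cannot replace step 1.
3. Have the system record that eligibility is confirmed before it releases the allocation, if it does not already, and reconcile sections 5.13 and 5.20 on an unreturned baseline urine sample so that no judgement is left at that step.

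The cost is a new list, a sentence in the protocol and a system check. The possible imbalance within a stratum rises from at most 2 to at most 4 per open block, which the stratum-adjusted model handles. If randomisation is already complete, the list cannot be changed.

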5.6 Blinding

It is not possible to blind study participants or researchers to who receives the salt reduction intervention. The study investigators will have no access to treatment allocations during the study. The primary and secondary outcomes will be measured objectively using home-based BP monitors, urine samples and scanned barcodes of packaged foods and beverages purchased, the latter which will be linked to a packaged food composition database to determine the sodium contents.

Not for Public Circulation or Reproduction

5.8 Withdrawal criteria

Participants will be informed that they may withdraw from the study at any time. They may also withdraw their data at any time. Data for withdrawn participants will be included in intention-to-treat analysis. The PI may withdraw a participant from the study if they feel it is in their best interest, or the study is terminated.

5.9 Participant referral

Interested people may be referred during recruitment in shopping malls, events, markets, pharmacies, on the Stroke Foundation BP bus, GP clinics, on social media and via market research panels. Study staff and healthcare providers at venues will complete a short referral form on the DIET website. Participant's height, weight and BP (average of at least two measures) will be collected and recorded along with their name, mobile number, email address, smartphone ownership, and consent to be contacted by the study team. Participants who are referred will be emailed a copy of the PIS. If the participant has expressed interest in the study via Facebook or a market research survey they will be contacted, screened and asked to attend a Grafton Clinic or directed to their local healthcare provider/participating Green Cross pharmacies to obtain required measurements.

5.10 Participant screening

Potentially eligible participants will receive a follow up phone call from a study RA and a screening questionnaire will be administered. The screening questionnaire will collect date of birth and gender (male, female, gender diverse, prefer not to specify), and information on remaining inclusion/exclusion criteria relevant to the screening period: type of smartphone, contribution to household grocery shopping (or willing to for the study period), able to read and understand English, current use of a dietary salt substitute or the FoodSwitch app, contraindication to reducing salt or increasing potassium in their diet, recent stroke or cardiovascular event, or diagnosed heart failure. Eligible participants will be sent a text link to download the study smartphone app.

5.11 Changes to referral and screening process due to Covid-19 – Addition of remote screening option

Due to Covid-19 and closure of The University of Auckland campuses until the end of July, a remote referral and screening process has been devised to allow the study to continue during this period and ensure the safety of study participants and staff. This remote screening option will be offered to any participants recruited through self-referral methods such as market research surveys and Facebook who are not able to attend a clinic for screening measurements. Instead of attending a face to face clinic the participant will be screened over the phone and, if eligible,

Not for Public Circulation or Reproduction

asked to self-report their weight and height. They may self-report these measures either by measuring them at home or by calling their GP if they have had a measure in the last three months. If they are unable to provide the measurements, they will be placed on hold until face to face clinics are deemed safe to proceed. If they can provide measurements, they will be couried a blood pressure monitor and guided over the phone by a Research Assistant to take three seated blood pressure measurements (one minute apart as per the protocol) and read these to the Research Assistant. The Research Assistant will then determine if the participant is eligible to proceed with the study based on the eligibility criteria and, if so, support the participant to progress to the consent and baseline phase of the study. If they are ineligible to proceed the Research Assistant will provide guidance on return of the blood pressure monitor. A flow diagram outlining the remote screening option process can be found in Appendix 5.

5.12 Informed consent

Following confirmation of eligibility, a study RA will make sure the participant has read and understood the PIS and will support the participant to download the study smartphone app and complete the consent form (all within the app). The consent form will include one question asking participants if they would be happy to be contacted after the study has finished, to assess longer term outcomes or to be invited to take part in other research studies. Participants who do not consent to this may still take part in the study. Auckland-based participants may be offered face-to-face screening at the University of Auckland Grafton clinics if necessary.

5.13 Baseline assessment

Baseline assessment will comprise four components: (1) the baseline questionnaire, (2) collection of twice-daily home-based BP measures during week -1 (+/- two weeks), (3) return of a spot (casual) urine sample during week -1 (+/- two weeks), and (4) scanning of barcodes for all packaged foods and beverages bought into the home for consumption during weeks -2 and -1 (+/- two weeks), (minimum 10 required).

Baseline questionnaire

Following consent, participants will be prompted in the study app to complete the baseline questionnaire. This may be done with the support of a study RA on the phone, or in the participant's own time. Two text reminders will be sent five days apart if required. If the baseline questionnaire has not been completed within four weeks following consent, the participant will be excluded from the study.

The baseline questionnaire will collect the following information:

- 1. Initials, date of birth
- 2. Type of smartphone
- 3. Discretionary salt intake
- 4. Preference for salty food
- 5. Usual take-away consumption
- 6. Use of nutrition labels when food shopping
- 7. Existing health conditions
- 8. Number living in household for which groceries are usually bought each week
- 9. Concurrent medications
- 10. Ethnicity participant most identifies with
- 11. Highest qualification
- 12. Employment status
- 13. Annual household income

Not for Public Circulation or Reproduction

Collection of a spot (casual) urine sample

Following completion of the baseline questionnaire, participants will be couriered a package containing equipment to collect a spot (casual) urine sample and a Wi-Fi enabled BP monitor (BlipCare). The barcode scanning functionality with the study smartphone app will also be activated at this time. A study RA will text/phone participants and guide them through short tutorials within the study smartphone app on how to collect urine samples, measure BP, and scan the barcodes of purchased packaged foods and beverages (or tutorials may be watched in the participants own time).

The spot (casual) urine sample will be collected by the participant at any time of the day during week -1 +/- two weeks), except first void. Participants will collect urine in a beaker with a pouring facility, which will be used to transfer ~5mL into a pre-labelled 10mL tube. Participants will freeze the sample before couriering it to researchers at The University of Auckland. Participants will be provided with a small bubble wrapped bag for the urine sample, and a same-day courier bag. Participants may keep their urine sample cool with a freezer pack rather than store it in the freezer or send it immediately by courier if they prefer. A study RA will log urine samples and store them at -4deg before couriering bulk samples to The University of Otago for analysis. Two text reminders to collect the urine sample will be sent per week for the two-week baseline period. If a urine sample has not been returned for the baseline period, these data will be considered missing.

Collection of BP

Blood pressure will be collected by the participant on a home-based automated Wi-Fi enable BP monitor using methods adapted from the PATHWAY-2 trial and according to European Society of Cardiology guidelines^{31,32}. Participants will collect BP measures in triplicate after 5 mins rest, 1 minute apart. Measures will be taken both morning and evening, ideally at the same time each day during week -1 +/- two weeks). Participants will receive twice-daily notifications to their phone to remind them to collect their BP. If no BP measures have been received by researchers within one week of the phone call to confirm receipt of the monitor, reminder notifications will be sent and the participant will receive a phone call from a study RA to ensure they are confident in using the monitor. If less than six BP measures have been received within two weeks following courier of the BP monitor, BP data will be considered missing, the participant will be excluded, and the BP monitor will returned to researchers. Blood pressure measures will be received in real time directly from participant's monitors via an Application Programming Interface (API). Consistently elevated SBP (>180mmHg for three consecutive days including any missing days), consistently low SBP (<90mmHg for three consecutive days including any missing days), or major changes in SBP from baseline (>20mmHg) will trigger a notification to be sent to the study staff. The RA will confirm this by investigating the raw data and call the participant advising them that their BP measure is outside the normal range and it is recommended that they visit their GP as soon as possible. The RA will send a letter to notify a participant's GP where required.

Collection of barcodes for packaged food purchases

Participants will scan the barcode of all packaged foods and beverages bought into the home for their consumption during the two-week baseline period (weeks -2 and -1 +/- two weeks). Weekly notifications will be sent to their phone via the study smartphone app to remind them to complete the scanning. Barcodes will be used as unique product identifiers for linking with the Nutritrack supermarket food composition database[30] to determine the sodium content of food purchases. If no shopping purchase information has been returned for the baseline period, these data will be considered missing.

